### 7.3 Interim Analysis

No interim analysis is planned for this study.

### 7.4 Pooling Strategy for Study Sites

With an overall study sample size of 30 patients distributed among six to ten study sites, the ideal distribution of patients is three to five patients in each study site.

For the purpose of the analysis of variance (ANOVA) for the primary and secondary endpoints, study sites with 3 or less patients will be combined in a way that the resulting study sites utilized in the analysis have similar patient numbers.

### 7.5 Visit Windows/Unscheduled Visits

All patients will be screened up to 24 hours prior to treatment. Treatment will consist of one CRRT session lasting no longer than 72 hours from the start of study treatment. For a detailed description of visit windows please reference Table 1 Schedule of Visits and Procedures as well as Table 2 Blood Sampling Schedule and Table 3 Vital Signs and Fluid Overload Assessment Schedule. Unscheduled visits, while not anticipated, will be considered for analysis depending on purpose and time point of measurement.

**Table 2. Blood Sampling Schedule** 

Solute	Prior to CRRT*	At Initiation of CRRT**	During CRRT	End of HF20 CRRT (if after 24 hours & between 12 hours interval)
Hemoglobin	Up to 24 hours prior to initiation of CRRT	As determined by local standard of care	As determined by local standard of care	N/A
BUN	Up to 24 hours prior to initiation of CRRT	Within 1 hour prior to or within 15 minutes after CRRT initiation.	At +/- 1 hour of 12, 24, 36, 48, 60 and 72 hours	Use previous 12 hours interval result
FUN	N/A	Within 1 hour prior to or within 15 minutes after CRRT initiation.	At +/- 1 hour of 12, 24, 36, 48, 60 and 72 hours	Use previous 12 hours interval result
Creatinine	Up to 24 hours prior to initiation of CRRT	Within 1 hour prior to or within 15 minutes after CRRT initiation.	At +/- 1 hour of 12, 24, 36, 48, 60 and 72 hours	Use previous 12 hours interval result
Bicarbonate	Up to 24 hours prior to initiation of CRRT	Within 1 hour prior to or within 15 minutes after CRRT initiation.	At +/- 1 hour of 12, 24, 36, 48, 60 and 72 hours.	Use previous 12 hours interval result
Sodium	Up to 24 hours prior to initiation of CRRT	Within 1 hour prior to or within 15 minutes after CRRT initiation.	At +/- 1 hour of 12, 24, 36, 48, 60 and 72 hours	Use previous 12 hours interval result
Potassium	Up to 24 hours prior to initiation of CRRT	Within 1 hour prior to or within 15 minutes after CRRT initiation.	At +/- 1 hour of 12, 24, 36, 48, 60 and 72 hours	Use previous 12 hours interval result
Chloride	Up to 24 hours prior to initiation of CRRT	Within 1 hour prior to or within 15 minutes after CRRT initiation.	At +/- 1 hour of 12, 24, 36, 48, 60 and 72 hours	Use previous 12 hours interval result
Phosphorous	Up to 24 hours prior to initiation of CRRT	Within 1 hour prior to or within 15 minutes after CRRT initiation.	At +/- 1 hour of 12, 24, 36, 48, 60 and 72 hours	Use previous 12 hours interval result
Albumin	Up to 24 hours prior to initiation of CRRT	Within 1 hour prior to or within 15 minutes after CRRT initiation.	At +/- 1 hour of 12, 24, 36, 48, 60 and 72 hours	Use previous 12 hours interval result
B2M	N/A	Within 1 hour prior to or within 15 minutes after CRRT initiation.	At +/- 1 hour of 24,48, and 72 hours	Use previous 12 hours interval result

Solute	Prior to CRRT*	At Initiation of CRRT**	During CRRT	End of HF20 CRRT (if after 24 hours & between 12 hours interval)
ACT (Applies to heparin use only)	N/A	As determined by local standard of care	As determined by local standard of care	As determined by local standard of care
PTT (Applies to heparin use only)	N/A	As determined by local standard of care	As determined by local standard of care	As determined by local standard of care
APTT (Applies to heparin use only)	N/A	As determined by local standard of care	As determined by local standard of care	As determined by local standard of care
Total Calcium	N/A	As determined by local standard of care	As determined by local standard of care	N/A
Extracorporeal Circuit ionized calcium (Not indicated when heparin or no anticoagulation are used)	N/A	N/A	As determined by local standard of care	N/A
Patient Ionized Calcium (Not indicated when heparin or no anticoagulant are used)	N/A	N/A	As determined by local standard of care	N/A

\* Labs up to 24 hours prior to CRRT are required, unless the patient presents directly to ICU with immediate need for CRRT. Patient must meet all laboratory based inclusion criteria prior to starting treatment.

\*\* "At initiation of CRRT" samples must be obtained within 1 hour prior to or within 15 minutes after treatment initiation. Labs drawn more than 1 hour prior to initiation will not be acceptable.

Table 3. Vital Signs and Fluid Overload Assessment Schedule

Parameter	Prior to CRRT	At Initiation of CRRT - Baseline	During CRRT	End of CRRT (& if prior to 72 hours)
BP (mmHg)	Within 24 hours prior to CRRT	Within 1 hour prior to or within 15 minutes after CRRT Initiation	Hourly (± 15 minutes)	End of Treatment (± 15 minutes)
MAP (mmHg)	Within 24 hours prior to CRRT	Within 1 hour prior to or within 15 minutes after CRRT Initiation	Hourly (± 15 minutes)	End of Treatment (± 15 minutes)
Degree of Fluid Overload*	Within 24 hours prior to CRRT	Within 1 hour prior to or within 15 minutes after CRRT Initiation	At +/- 1 hour of 12, 24, 36, 48, 60, & 72 hours	End of Treatment (± 15 minutes)

\* Degree of Fluid Overload assessment = [fluid intake (L) - fluid output (L) / ICU admission weight (Kg)]×100%

\*\* Re-assess and record baseline measurements if CRRT is being re-initiated (clot/interruption)

### 7.6 Other Issues

Not applicable.

### 8. DEMOGRAPHICS AND BASELINE CHARACTERISTICS

Demographic and baseline characteristics will be summarized using descriptive statistics for all subjects as well as for each clearance specification subgroups (if applicable).

Demographic data include age, gender, race, ethnicity, height, weight at hospital admission, body surface area and calculated intravascular blood volume. Calculated intravascular blood volume will be calculated as 70 ml multiplied by the patient's hospital admission weight in kilograms.

Baseline characteristics collected on the eCRF also include medical history and acute kidney injury history. Acute kidney injury (AKI) history recorded data will include: cause of AKI, current ICU diagnosis, prior CRRT treatment, and end date and time of last CRRT treatment.

Lab data including: serum sodium, potassium, chloride, bicarbonate, serum creatinine, phosphorus, total calcium, albumin, beta 2 microglobulin, BUN, and FUN are collected at baseline as well as at screening and every 12 hours for up to 72 hours after CRRT initiation. Vital sign data including: temperature, systolic/diastolic blood pressure, mean arterial pressure, pulse, and respiratory rate are captured at baseline as well as screening and hourly up to 72 hours after CRRT initiation. Mechanically ventilated patients will also be recorded every 12 hours after initiation of CRRT.

The following describes the summary of various types of demographic and baseline data either as continuous data, frequency tabulations or as listings:

- 1. Age, height, hospital admission weight, body surface area, and calculated intravascular blood volume will be summarized as a continuous variable.
- 2. The frequencies for gender, race and ethnicity will be tabulated.
- 3. Medical conditions and surgery items recorded in the medical history eCRF will be coded to a Medical Dictionary for Regulatory Activities (MedDRA, Version 16.1 or higher) and listed by system organ class and preferred term
- 4. AKI history will be listed for each patient.
- 5. All laboratory samples collected at baseline will be summarized as continuous variables for both analysis populations.

6. All vital sign values collected at baseline will be summarized as continuous variables populations except for the number of patients mechanically ventilated at baseline which will be presented as a frequency and percentage.

Continuous data will typically be summarized using the number of patients (n), mean, standard deviation, minimum, median, and maximum, while categorical data will be presented by frequency count and percentage.

# **9. ANALYSIS OF PHARMACOKINETICS AND PHARMACODYNAMICS** Not applicable.

### 10. TREATMENT COMPLIANCE AND EXPOSURE

Treatment compliance will be provided in listings and summarized as a frequency of both, patients that started CRRT, and those patients which had a measurement taken at the 24 hours time point. The patients with both baseline and 24 hours time point measurements will also be summarized as frequency counts. The total time of CRRT will also be summarized as a continuous variable for both population sets. Treatment compliance and exposure will be summarized for both the Full Analysis Set and Per Protocol Set.

# 11. CHANGES IN CONDUCT OR PLANNED ANALYSES FROM THE PROTOCOL

All the changes in the planned analysis have been agreed upon Baxter and the FDA in a pre-submission meeting on February 27, 2018:

- Subgroup analysis will be added due to the HF20 Set used in this study may have two specification limits. (See Section 12.6 for explicit details.)
- Missing data imputation will be performed. (See Section 7.2 for explicit details.)
- Primary endpoint will use the FAS as primary analysis; and use the PPS as supportive analysis. (See Section 12.1 and Section 12.2 for explicit details.)
- Statistical testing for the 24 hours percentage reductions of creatinine and bicarbonate from baseline will be removed.

### 12. EFFICACY PARAMETERS

### 12.1 Primary Analysis

The primary analysis will be to demonstrate a mean reduction of greater than 38% in BUN at 24 hours from initiation of CRRT. This percentage of reduction is motivated by

the target of getting patients with an initial BUN of 80 mg/dL below 50 mg/dL after 24 hours of treatment.

The hypothesis to be tested is:

$$H_0$$
:  $\mu \leq 38\%$ ,

$$H_a$$
:  $\mu > 38\%$ 

Where  $\mu$  stands for the mean percentage reduction in BUN from baseline to 24 hours calculated as:

$$\mu = \frac{BUN_{0hr} - BUN_{24hr}}{BUN_{0hr}} \times 100\%$$

Where BUNohr is BUN recorded at baseline and BUN24hr is BUN recorded at 24 hours after CRRT initiation.

This hypothesis will be tested using a one-sample t test and the actual mean percentage reduction in BUN will be quantified using a 95% confidence interval.

As a supportive analysis, an analysis of variance (ANOVA) will be implemented to investigate the mean change from baseline among the different sites.

A box plot will also be generated to represent the 24 hours change in BUN from baseline.

The primary analysis of the primary endpoint will be based on the FAS. As supportive analysis, the same analysis will be carried out on the PPS.

### 12.2 Sensitivity Analysis

The analysis of the primary endpoint using the PPS will be considered as a part of sensitivity analyses.

Subgroup analysis (if applicable) will be also considered as a part of sensitivity analyses.

The impact of missing data on the primary analysis will be further explored as sensitivity analyses using statistical imputation approaches. (See Section 7.2 for explicit details.)

### 12.3 Secondary Analysis

The percent change from baseline to 24 hours after treatment initiation in creatinine and TCO2 will be summarized descriptively.

The survival time of the Prismaflex HF20 Set will be analyzed using a Kaplan Meier survival curve to generate the median (0.50), 1st (0.75) and 3rd (0.25) quartile survival times after the start of CRRT.

The life of a filter that is replaced due to continuous use for 72 hours will be censored for the statistical analysis of this secondary endpoint. Filters that are replaced any time CRRT is stopped for reasons other than the failure to medicate the two alarms specified in Section 5.1 will be censored at their current duration of usage. Only filters that are replaced due to the two alarms (filter clotted, and TMP excessive) shall be considered events for this survival analysis.

Box plots will also be generated to represent the 24 hours percent change in creatinine and TCO2 from baseline.

The secondary analysis will be carried out on the FAS and PPS.

# 

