5.3 Prismaflex System Software Version 7.10 and 7.20 Alarm System for UF Errors

Prismaflex System Software Version 7.10 and 7.20 alarms will be issued based on immediate deviations between delivered and expected fluid weight on each bag of >20 g. A treatment shutdown will be issued and alarm given based on the cumulative UF error in a 3 hour sliding window.

The determination of an acceptable Prismaflex System Software Version 7.10 and 7.20 UF error limit follows from the UF rate error, which is not to exceed 0.1 mL/kg/min in order to avoid complications, up to and including hemodynamic instability. The UF error limit default is determined based on the cumulative UF rate error over a sliding 3 hours window. The Patient Fluid Removal accuracy (PFR acc) of the Prismaflex System Software Version 7.10 and 7.20 is considered in this interval (± 70 mL per 3 hours):

UF default error limit = $0.1 \text{ mL/kg/min} \times 180 \text{ min} \times BW - PFR$ acc

This default UF error limit is calculated based on the patient weight entered during the set-up phase of the treatment. As an example, a patient weight of 10 kg would result in a default error limit of:

UF default error limit = $0.1 \text{ mL/kg/min} \times 180 \text{ min} \times 10 \text{ kg} - 70 \text{ mL} = 110 \text{ mL}$

Determination of the actual limit may follow the calculated default value, but is ultimately up to the discretion of the prescribing physician investigator. In consideration of the patient's condition, a more stringent limit may apply.

The prescribed limit is settable down to a limit of 60 mL/3 hours and is entered by the device operator. This is a mandatory action in order to be able to proceed to patient connection. Once set, the UF error limit is active throughout the treatment.

Should the preset UF error limit be reached during treatment, the device monitoring system will issue an alarm and terminate the treatment. Treatment at this point cannot be re-started on the same filter. Occurrence of such events shall prompt a call to the investigator and should alert the personnel to reassess the patient before continuation of the treatment on a new disposable set.

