5.8.2.10 Prismaflex Alarms Related to Fluid Balance

- 1. Alarm type (Caution: Flow Problem, Caution: Loss Limit Reached or Caution: Gain Limit Reached)
- 2. Operator Set Limit for Unintended Patient Fluid Loss/Gain (mL/1h)

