### 4.2 Secondary Objectives

The secondary objectives of this study are:

- To evaluate the efficacy of removing creatinine and normalizing bicarbonate.
- To evaluate the safety of the Prismaflex System Software Version 7.10 and 7.20 in pediatric AKI patients weighing  $\geq 8$  and  $\leq 20$  kg (ie,  $\geq 17.6$  and  $\leq 44.09$  lbs).
- To determine how long a duration of time each Prismaflex HF20 Set can be used up to a maximum of 72 hours from the initiation of CRRT.

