### **5.6 Safety Measures**

While no formal primary safety analysis is planned for this study, one of the secondary endpoints is the safety of the Prismaflex System in pediatric AKI patients. Adverse Events (AEs) and Serious Adverse Events (SAEs) along with device deficiencies will be continuously collected throughout the study (up to 72 hours after treatment initiation on the final HF20 Set).

The following alarms from Prismaflex System Software Version 7.10 or 7.20 related to fluid balance will be noted and recorded for:

- "Caution: Flow Problem",
- "Caution: Gain Limit Reached",
- "Caution: Loss Limit Reached".

The weight, state of uremia, cardiac status and general physical condition of the patient must be carefully evaluated and recorded by the prescribing physician as required and, at a minimum, each day during treatment.

Fluid overload will also be calculated and reported at baseline and every 12 hours after until treatment completion.

Patient CRRT treatment prescription will be recorded at CRRT initiation and at the beginning of each visit window (every 12 hours) for up to 72 hours. Values recorded will include: CRRT modality, blood prime used, CRRT anticoagulation, blood flow rate, preblood pump flow rate, PBP brand name/manufacturer, PBP formulation, dialysate flow rate, dialysate brand name/manufacturer, dialysate formulation, post filter replacement flow rate, post filter fluid formulation, use of anticoagulation, anticoagulation formulation and anticoagulation rate.

Patient CRRT values will be collected every hour and include: TMP, prescribed patient fluid removal rate, actual period fluid removal, total fluid removal, actual unintended patient fluid gain/loss, prescribed unintended patient fluid gain/loss, and prescribed effluent rate.

Post treatment outcome data will be collected upon the completion of study CRRT and includes: Pediatric Intensive Care Unit (PICU) outcome, total prescribed dose, total delivered dose, dry weight and metabolic control attained and the patient's survival status.

Lab values will be collected at screening and CRRT initiation and will be taken every 12 hours for up to 72 hours after CRRT initiation. Any lab values which are considered abnormal clinically significant will be recorded as an adverse event.

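### The planned filter-life curve estimates time to a clotting or TMP alarm, not how long a set can be used, because sets ended by a UF-error-limit shutdown are censored

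*SAP*

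**What the plan says.** **Objective.** SAP 4.2 lists as a secondary objective: "To determine how long a duration of time each Prismaflex HF20 Set can be used", to a maximum of 72 hours. SAP 5.5.2 measures circuit life from start of treatment to the time the patient comes off the set, less interruptions, without restricting the cause.

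**Events and censoring.** SAP 12.3 plans a Kaplan-Meier curve with median and quartiles. On events it says: "Only filters that are replaced due to the two alarms (filter clotted, and TMP excessive) shall be considered events for this survival analysis". Filters replaced when CRRT stops for other reasons "will be censored at their current duration of usage". For the time limit: "The life of a filter that is replaced due to continuous use for 72 hours will be censored". The two-alarm definition of end of circuit life also stands in the protocol (Synopsis, Section 3 and Appendix 1) and in SAP 5.1.

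**The other device-forced end.** Protocol 5.3: "Should the preset UF error limit be reached during treatment, the device monitoring system will issue an alarm and terminate the treatment". It continues: "Treatment at this point cannot be re-started on the same filter". Any continuation is on a new set.

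**Where such shutdowns would be reported.** The fluid-balance alarms, including "Caution: Gain Limit Reached" and its Loss Limit counterpart, are recorded as safety data (SAP 5.6) and are counted and listed (SAP 13.2). No planned output links them to set life.

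**The concern.** A set that the machine has ended for good has no usable life left. Censoring it treats the end of its life as unobserved, so the curve describes sets in a setting where this kind of shutdown does not happen. That is a different quantity from the one named in the objective.

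The study supports a 510(k) submission. A reader who sees a median set life under that objective will naturally take it as how long a set lasts in use. SAP 12.2 confines its sensitivity analyses to the primary endpoint. The filter-life outputs in the SAP's table lists are survival summaries, with no competing-risk or all-device-end version. The text of SAP 12.4 is not visible, but the titles of Tables 14.2.4.1 and 14.2.4.2 concern clearance and bicarbonate, not set life.

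**Working it through.** The documents give no expected median, event count or shutdown rate for set life, so there is no planned figure to reproduce. What can be checked is the direction and, under stated assumptions, the size.

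**1. Direction (no distributional assumption).** Without ties, the Kaplan-Meier estimate multiplies (1 - 1/n) over event times, where n is the number of sets at risk. Recoding a shutdown from censored to event leaves every risk set unchanged, because the set leaves at the same time either way. Hence:

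S(shutdowns counted) = S(planned) × product over shutdowns of (1 - 1/n).

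Each added factor is below 1, so the planned curve is at or above the other from the first shutdown on. With no shutdown the two are identical.

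**2. Size under constant hazards (assumed).** Let λ be the total hazard of a permanent alarm end (the two alarms plus UF-error-limit shutdown) and f the share due to the shutdown.

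- Planned curve: exp(-(1-f)λt), median ln 2/((1-f)λ).
- Shutdowns counted: exp(-λt), median ln 2/λ.
- Ratio of medians: 1/(1-f).

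Illustration with an assumed median of 48 h when shutdowns are counted, so that 72-h survival is 2^(-72/48) = 35.4%:

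| f (assumed) | 1/(1-f) | Planned median | Planned 72-h survival |
|---|---|---|---|
| 0 | 1.00 | 48.0 h | 35.4% |
| 5% | 1.05 | 50.5 h | 37.2% |
| 10% | 1.11 | 53.3 h | 39.2% |
| 20% | 1.25 | 60.0 h | 43.5% |
| 30% | 1.43 | 68.6 h | 48.3% |

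**3. At the trial's scale (all inputs assumed).** Thirty sets, 12 two-alarm events, k shutdowns, the rest censored at 72 h, stop times uniform on 2 to 70 h, 4,000 simulated data sets for each k. With shutdowns counted, 72-h survival is exactly (18-k)/30.

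| k | 72-h survival, planned | 72-h survival, counted | First-quartile time, planned | First-quartile time, counted |
|---|---|---|---|---|
| 1 | 59.2% | 17/30 = 56.7% | 43.9 h | 40.8 h |
| 3 | 57.4% | 15/30 = 50.0% | 43.6 h | 36.1 h |
| 6 | 54.3% | 12/30 = 40.0% | 41.4 h | 30.3 h |

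The planned curve was at or above the other in every simulated data set.

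**4. Can such shutdowns be ruled out from the documents?** Protocol 5.3 gives the default limit as 0.1 mL/kg/min × 180 min × weight - 70 mL. At 10 kg this is 180 - 70 = 110 mL, matching the protocol's example. At 8 kg it is 144 - 70 = 74 mL, and at 20 kg, the upper bound, 360 - 70 = 290 mL. The fluid-removal accuracy quoted in the same section is ±70 mL per 3 hours, and the limit can be set as low as 60 mL per 3 hours. This yields no rate, but it means a zero rate cannot be presumed.

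**5. Which alarm is it?** Protocol 5.3 does not name the alarm issued at the UF error limit. Protocol 5.8.2.10 records the operator-set limit on unintended fluid loss or gain beside the Gain and Loss Limit alarms, so these are apparently the same event. That is an inference. Two inconsistencies stand in its way: the Gain and Loss alarms are Warnings in the Synopsis but Cautions in Protocol 3 and 5.8.2.10 and SAP 5.6, and the limit is per 3 hours in Protocol 5.3 but per 1 hour in 5.8.2.10.

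**The case against.** The strongest reply is that this compares two estimands and shows no error. The protocol defines end of circuit life by the two alarms, and SAP 12.3 applies that definition openly. If shutdowns are unrelated to impending clotting, censoring them gives a correct estimate of time to clotting/TMP failure, and 1/(1-f) is simply the gap between two endpoints. There is also a reason for the split: the UF error limit is entered by the operator at the physician's discretion, so a tighter limit would shorten set life with no change in the filter. Shutdowns are not hidden either, since alarms are tabulated and filter life is listed for all subjects. The endpoint is secondary and descriptive, with no success threshold.

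Most of this stands, and it limits the point. A reader might infer that the planned curve is biased, or that the censoring is informative. The documents do not support that: no passage ties a fluid-balance shutdown to clotting, f is not given and may be zero, and the link to the Gain and Loss Limit alarms is inferred.

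What the reply does not remove is the mismatch between the objective and the one curve planned to address it. Protocol 5.3 says the set is finished, SAP 5.5.2 times it to the moment it comes off, and SAP 12.3 then codes that moment as censored. Listings would let a reader reconstruct the other curve, but that is no substitute for fixing its definition in advance.

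**Conclusion.** The point holds as a gap between the stated objective and the planned estimand, not as an error in the planned Kaplan-Meier. SAP 12.3 estimates time to an unmitigated clotting or TMP alarm. If at least one UF-error-limit shutdown occurs while sets are at risk, the reported curve will lie at or above the curve of actual usable life. That direction follows from the product-limit formula alone.

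The size cannot be determined from the documents. The factors 1.11 at f = 10% and 1.25 at f = 20% rest on constant hazards and assumed shares, and at f = 0 there is no difference. The flat statement that the analysis overstates set life goes further than the documents allow. The primary BUN analysis is not touched. This is an inexpensive improvement worth making before the data are analysed.

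**What to change.** In SAP 12.3:

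1. Keep the two-alarm curve and label it as time to clotting/TMP failure.
2. Pre-specify a supplementary curve in which every non-elective, device-related permanent end of a set is an event: Filter Clotted, TMP Excessive, UF-error-limit shutdown, and other device-related ends such as a dialyzer blood leak. Censor only elective stops, death, transfer and the 72-hour limit. Assign each recorded stop reason to one side beforehand, so that none is left unclassified.
3. Add cumulative incidence by cause (Aalen-Johansen) and a table of stop reasons, and report both medians side by side.
4. Reconcile the Warning/Caution naming and the 3-hour versus 1-hour limit units across the Synopsis, Protocol 3, 5.3 and 5.8.2.10 and SAP 5.6, and state which alarm marks a UF-error-limit shutdown, so that these ends can be identified in the data.

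The data are already collected: reasons and times for interruptions and filter changes (Protocol 5.8.2.8), alarm types (5.8.2.10) and machine log files (5.5.1). The cost is one extra table and curve, and possibly a less favourable secondary figure. Neither the protocol's endpoint definition nor patient management changes.
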